2 SCHEDULE OF ACTIVITIES

Table 2-1: Screening Procedural Outline (Safety Run-in Phase and Randomized Phase; CA2097A8)

Procedure ^a	Screening Visit	Notes All windows are based on calendar days.
Eligibility Assessments		
Informed Consent	X	Must be obtained prior to any study-related procedures. Register in IRT system to obtain participant number.
Inclusion/Exclusion Criteria	X	Must be assessed at screening and must be confirmed prior to: 
 • Safety Run-in participants: first dose • Randomized participants: randomization
Medical History	X	All medical history relevant to the disease under study, including tobacco history.
Documentation of Postmenopausal Status	X	Please see inclusion criterion 3) b) in Section 6.1 (Inclusion Criteria) for a definition of postmenopausal women.
Pretreatment Tumor Sample Submission	X	
A recent archival tumor biopsy (collected within 90 days prior to enrollment) is required in the format of FFPE block (strongly preferred) or 22 unstained tumor slides (sectioned within 60 days prior to enrollment from a tissue sample collected within 90 days prior to enrollment). If a recent tumor specimen is not available, a fresh tumor biopsy collection is required. At least 15 unstained slides must be submitted for a participant to be eligible. If < 15 unstained slides are available, the participant is not eligible.
 
 • Safety Run-in participants: Participant can start study treatment before confirmation of receipt of the tumor sample by the central laboratory. However, receipt of the tumor sample by the central laboratory must occur within 28 days of the first dose. 

Safety Assessments		
Targeted PE, Measurements, Vital Signs, and ECOG PS	X	Height, weight, BP, HR, RR, temperature, and ECOG PS (Appendix 5). Must be collected within 14 days prior to: 
 • Safety Run-in participants: first dose

Table 2-1: Screening Procedural Outline (Safety Run-in Phase and Randomized Phase; CA2097A8)

Procedure ^a	Screening Visit	Notes All windows are based on calendar days.
		
 • Randomized participants: randomization • Targeted PE must include ocular examination.
ECG	X	Must be performed within 28 days prior to: 
 • Safety Run-in participants: first dose • Randomized participant: randomization
ECHO (preferred) or MUGA	X	Must be performed within 28 days prior to: 
 • Safety Run-in participants: first dose • Randomized participants: randomization
Assessment of Signs and Symptoms	X	Must be performed within 14 days prior to: 
 • Safety Run-in participants: first dose • Randomized participants: randomization
Concomitant Medication Use	X	Must be performed within 14 days prior to: 
 • Safety Run-in participants: first dose • Randomized participants: randomization Vaccine use within 30 days prior to first dose.
Chest X-ray	X	Must be performed within 14 days prior to: 
 • Safety Run-in participants: first dose • Randomized Phase participants: randomization
SAE Assessment	X	SAE collection from time of consent.
Laboratory Tests		
CBC with Differential, Chemistry, Endocrine, and Serology	X	Must be performed within 14 days prior to: 
 • Safety Run-in participants: first dose • Randomized Phase participants: randomization FSH and Estradiol are required for women ≤ 55. See Section 9.4.4 for a list of laboratory tests to conduct.

Table 2-1: Screening Procedural Outline (Safety Run-in Phase and Randomized Phase; CA2097A8)

Procedure ^a	Screening Visit	Notes All windows are based on calendar days.
Efficacy Assessments		
Documentation of Planned Surgery	X	Record type of planned BC surgery (ie, BCS, mastectomy).
Clinical Breast Examination	X	Clinical breast examination by palpation of breast and axilla.
Breast and Axilla Ultrasound (Preferred) or Mammogram	X	Perform breast and axilla ultrasound (preferred) or a mammogram within 28 days prior to: 
 • Safety-run in participants: first dose • Randomized participant: randomization • Every attempt should be made to image each participant using an identical imaging modality and acquisition protocol for all imaging time points.
Other Imaging (eg, Bone Scan)	X	As clinically indicated per local standards, including pathologic examination of suspected lesions. See Section 9.1 (Efficacy Assessments) for further details.
Axillary Lymph Nodes Fine Needle Biopsy or Core Biopsy	X	This procedure at screening will be omitted if there is no suspicion for positive axillary lymph node(s) radiographically, or if a pathological report of suspicious lymph nodes of the results of a fine needle biopsy or core biopsy are available prior to the Screening Period.

Abbreviations: BC = breast cancer; BCS = breast-conserving surgery; BP = blood pressure; CBC = complete blood count; ECG = electrocardiogram; ECHO = echocardiogram; ECOG = Eastern Cooperative Oncology Group; eCRF = electronic case report form; ER = estrogen receptor; FFPE = formalin-fixed, paraffin-embedded; FSH = follicle-stimulating hormone; HR = heart rate; IHC = immunohistochemistry; IRT = Interactive Response Technology; MUGA = multiple gated acquisition; ██████████ PE = physical examination; PS = performance status; RR = respiratory rate; SAE = serious adverse event.

^a Some of the assessments referred to in this section may not be captured as data in the eCRF. They are intended to be used as safety monitoring by the treating physician. Additional testing or assessments may be performed as clinically necessary or where required by institutional or local regulations.

Table 2-2: On-treatment Pre-surgery (Neoadjuvant) Procedural Outline (Safety Run-in Phase and Randomized Phase; CA2097A8)

Procedure ^a	Neoadjuvant Treatment ^{b,c} Cycle 1-5 (1 cycle = 4 weeks)				Pre-surgery (within 7 days prior to surgery)	Notes ^d
	Day 1	Day 8	Day 15	Day 22		
Safety Assessments						
Targeted PE, Measurements, Vital Signs, and ECOG PS	X		C2D15 (see Notes)		X	Weight, BP, HR, temperature, and ECOG PS (Appendix 5) on Day 1 of each cycle. Targeted PE must also include ocular examination at C1D1, C2D15, and as clinically indicated.
Pulse Oximetry	X (predose)					For each testing, two measurements are needed, i.e. at rest and immediately post ambulation
ECG	C1D1 (predose)		C1D15 (predose)			Triplicate ECG (collected within ~ 5 minute window) at C1D1, C1D15, and as clinically indicated.
AEs Assessment (including SAEs)	Continuously.					Record at each visit.
Concomitant Medication Review	Continuously.					Record at each visit.
Laboratory Tests						
CBC with Differential, Chemistry Panel, and Endocrine Testing	X		X C1-C2			Must be performed within 3 calendar days prior to dosing for all time points, except C1D1, which does not need to be repeated if performed within 7 days prior to the first dose. See Section 9.4.4 (Clinical Safety Laboratory Assessments) for list of laboratory tests.
Efficacy Assessments						
Clinical Breast Examination	X					Clinical breast examination by palpation of breast and axilla.

Table 2-2: On-treatment Pre-surgery (Neoadjuvant) Procedural Outline (Safety Run-in Phase and Randomized Phase; CA2097A8)

Procedure ^a	Neoadjuvant Treatment ^{b,c} Cycle 1-5 (1 cycle = 4 weeks)				Pre-surgery (within 7 days prior to surgery)	Notes ^d
	Day 1	Day 8	Day 15	Day 22		
Breast and Axilla Ultrasound (Preferred) or Mammogram	C2D22 (as clinically indicated)				X	Breast and axilla ultrasound (preferred) or mammogram to be done on C2D22 and within 7 calendar days prior to surgery. Every attempt should be made to image each participant using an identical imaging modality and acquisition protocol for all imaging time points.
Documentation of Actual Breast Surgery	See Notes.					Record actual type of BC surgery (ie, BCS, mastectomy) on day of or within 7 days after surgery.

Table 2-2: On-treatment Pre-surgery (Neoadjuvant) Procedural Outline (Safety Run-in Phase and Randomized Phase; CA2097A8)

Procedure ^a	Neoadjuvant Treatment ^{b,c} Cycle 1-5 (1 cycle = 4 weeks)				Pre-surgery (within 7 days prior to surgery)	Notes ^d
	Day 1	Day 8	Day 15	Day 22		
Study Drug						
Randomization	X					First dose to be administered within 3 calendar days following randomization (for Randomized Phase ONLY).
IRT Drug Assignment	X					Register the visit in the IRT for study drug allocation.

Table 2-2: On-treatment Pre-surgery (Neoadjuvant) Procedural Outline (Safety Run-in Phase and Randomized Phase; CA2097A8)

Procedure ^a	Neoadjuvant Treatment ^{b,c} Cycle 1-5 (1 cycle = 4 weeks)				Pre-surgery (within 7 days prior to surgery)	Notes ^d
	Day 1	Day 8	Day 15	Day 22		
Administer Nivolumab 480 mg (Safety Run-in Cohorts and Arms A and B)	X					To be administered Q4W IV. First dose to be administered within 3 calendar days following randomization. 
 • Randomized Phase: • Arm A and Arm B • Starting at C2D1 for Arm B
Dispense Anastrozole 1 mg and Provide and Review Patient Diary (Safety Run-in Cohorts and all Arms)	X					To be administered QD PO, with or without food. Review patient diary at each study visit. Note: Anastrozole given beyond C5 or beyond EOT will not be considered as study treatment and must be collected as concomitant medication.
AND						
Dispense Abemaciclib and Provide/Review Patient Diary (Safety Run-in Cohort 1) ^e	X					To be administered BID PO with or without food. Review patient diary at each study visit.
OR						
Dispense Palbociclib and Provide/Review Patient Diary (Safety Run-in Cohort 2 and Arms A, B, and C)	X					To be administered QD PO with food during the first 3 weeks of each cycle (1 week off). Review patient diary at each study visit.

Abbreviations: AE = adverse event; BC = breast cancer; BCS = breast-conserving surgery; BID = twice daily; BP = blood pressure; C = cycle; CBC = complete blood count; D = day; ECG = electrocardiogram; ECOG = Eastern Cooperative Oncology Group; eCRF = electronic case report form; EOT = end of treatment; HR = heart rate; IRT = interactive response technology; IV = intravenous; mg = milligram; PE = physical examination; PO = per os, (by mouth); PS = performance status; QD = daily; Q4W = every 4 weeks; SAE = serious adverse event.

[figure not shown]
- a The schedule for each procedure should coincide with actual dosing.
 - b Participants will undergo surgical treatment within 4 weeks of the last dose of neoadjuvant treatment (IV or oral, whichever comes later).
 - c On-treatment procedures may generally be performed within a ± 3 -day window, unless otherwise specified (eg, breast ultrasound or mammogram, tumor biopsy).
 - d Some of the assessments referred to in this section may not be captured as data in the eCRF. They are intended to be used as safety monitoring by the treating physician. Additional testing or assessments may be performed as clinically necessary or where required by institutional or local regulations.
- 

Table 2-3: Follow-up Procedural Outline (Safety Run-in Phase and Randomized Phase; CA2097A8)

Procedure	30-Day Safety Follow Up (FU1) ^a (± 7 days) (All Participants in the Safety Run-in Phase and the Randomized Phase)	100-Day Safety Follow Up (FU2) ^a (± 7 days) (All Participants in the Safety Run-in Phase and Arms A and B Only in the Randomized Phase)	Notes ^b
Safety Assessments			
Targeted PE, Measurements, Vital Signs, and ECOG PS	X	X	Weight, BP, HR, temperature, and ECOG PS. Targeted PE may include ocular examination, if clinically indicated.
AE Assessment (including SAEs)	X	X	Participants will be followed for treatment-related toxicities until these toxicities resolve, return to baseline, or are deemed irreversible. Note: All AEs will be documented for a minimum of 100 days after last dose of nivolumab for Safety Run-in Cohorts and Arms A and B, and for 30 days from the last dose of study treatment for Arm C.
Concomitant Medication Review	X	X	Record at each visit.
Subsequent Cancer Treatment	X	X	At each visit, record any new surgery, radiotherapy, and systemic cancer therapy given for the disease under study.
Laboratory Tests			
CBC with Differential, Chemistry, and Endocrine	X	X	Must be performed at FU1. If study drug-related toxicities persist, must be repeated at FU2. See Section 9.4.4 (Clinical Safety Laboratory Assessments) for list of laboratory tests to conduct.

Abbreviations: AE = adverse event; BP = blood pressure; CBC = complete blood count; ECOG = Eastern Cooperative Oncology Group; eCRF = electronic case report form; FU1 = follow-up visit 1; FU2 = follow-up visit 2; HR = heart rate; ██████████ IV = intravenous; PE = physical examination; ██████████ PS = performance status; SAE = serious adverse event; SOC = standard of care.

^a Participants must be followed for at least 100 days after last dose of nivolumab. FU1 should occur 30 days (± 7 days) from the last dose of any treatment (IV or oral whichever comes later). FU2 occurs approximately 100 days (± 7 days) from last dose of nivolumab. Both follow-up visits should be conducted in person.

^b Some of the assessments referred to in this section may not be captured as data in the eCRF. They are intended to be used as safety monitoring by the treating physician. Additional testing or assessments may be performed as clinically necessary or where required by institutional or local regulations.

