4 OBJECTIVES AND ENDPOINTS

Table 4-1: Objectives and Endpoints

Objectives	Endpoints
Primary	

 Safety Run-in Phase: Number of participants with occurrence of DLT. 	
 DLT is defined as TEAE (graded according to the NCI CTCAE v5.0) that occurs during the first 4 weeks after treatment start and that meets specific criteria (see Section 5.1.2.1).

 Randomized Phase: To assess RCB 0-I rate by central assessment of palbociclib plus anastrozole with or without nivolumab in all participants with untreated primary BC ≥ 2 cm (ER+, HER2-). 	
 RCB 0-I rate assessed by central assessment at the time of definitive surgery. RCB is a continuous index combining pathological measurements of primary tumor (size and cellularity) and nodal metastases (number and size) defined by a point system at surgery (refer to Appendix 7 [RCB Methods]).
Secondary	

 To assess the safety and tolerability of palbociclib plus anastrozole with or without nivolumab. 	
 Incidence of AEs, SAEs, AEs leading to discontinuation, immune-related AEs, deaths, and laboratory abnormalities in all participants.

 To assess pCR rate by local assessment of palbociclib plus anastrozole with or without nivolumab in participants with untreated primary BC ≥ 2 cm (ER+, HER2-). 	
 pCR rate in all participants assessed by the local pathologist at the time of definitive surgery. 
 pCR, defined as no invasive residual disease in breast or lymph nodes (ie, ypT0/is, ypN0) in the current AJCC staging system.

 To assess ORR (clinical and radiological [ultrasound (preferred) or mammography]) by Investigator assessment and BCS rate of palbociclib plus anastrozole with or without nivolumab in participants with untreated primary BC ≥ 2 cm (ER+, HER2-). 	
 ORR is defined as the number of participants with a BOR of CR or PR divided by the number of randomized participants for each treatment group at the end of the study treatment period. BCS rate is defined as the number of participants who undergo BCS after completing the study treatments divided by the number of randomized participants for each treatment group.

Table 4-1: Objectives and Endpoints

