[figure not shown]
In the Randomized Phase, participants will be randomly assigned by an IRT system to 3 different treatment arms and stratified by the following factors:

2) evaluation of lymph nodes (cytologically positive vs radiologically or cytologically negative); and 3) tumor size (> 3 cm or ≤ 3 cm).

For both the Safety Run-in Phase and Randomized Phase, participants will be treated for a maximum of 5 cycles (1 cycle = 4 weeks). Participants with progressive disease prior to completion of the 5-cycle study treatment must discontinue all study drugs and proceed to the Safety Follow-up Period. Participants who permanently discontinue the study drugs for any reason are considered to have completed the On-treatment Pre-surgery (neoadjuvant) Period, and hence reach end of treatment (EOT). After Cycle 5 or EOT, participants must continue to receive anastrozole (as concomitant medication and not as study treatment) until subsequent SOC breast surgery. Following the completion of neoadjuvant treatment, all participants who remain operative candidates will undergo definitive surgery for BC within 4 weeks of the last neoadjuvant treatment administration. If anastrozole can no longer be administered after EOT, participants will go to breast surgery right away. Pre-surgical lymph node biopsy is not allowed. Information on the type of the surgery will be collected and recorded in the electronic case report form (eCRF). Surgical specimens will be collected for the analyses outlined in the protocol. Depending on treatment assignment, up to 2 safety follow-up visits will be conducted in person. The first safety follow-up visit (FU1) will be completed for all participants within 30 days (± 7 days) from the last study treatment (oral or intravenous [IV], whichever occurs later). The second safety follow-up visit (FU2) will occur approximately within 100 days (± 7 days) from the last dose of nivolumab and will be required for participants in the Safety Run-in Phase and participants randomized to Arms A or B in the Randomized Phase. Further planned treatment of participants in the adjuvant setting (ie, radiotherapy, endocrine treatment, chemotherapy or any other treatment modality) will be at the discretion of the treating physician, following local clinical guidelines, and collected in the appropriate eCRF.

The study design schematic is presented in [Figure 5.1-1](#).

Figure 5.1-1: Study Design Schematic

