7.1.2 CDK4/6 Inhibitors and Anastrozole Dosing

Premedications are not recommended for the first dose.

In the Safety Run-in Phase, participant assignment to abemaciclib or palbociclib will be carefully managed by the study team with the Investigator. The selected CDK4/6 inhibitor cannot be changed or switched to another one once the study treatment has been initiated. At implementation of Revised Protocol 03, the study will only evaluate the combination of nivolumab with palbociclib plus anastrozole. Patients in screening and not yet treated were offered the option to join the nivolumab + palbociclib + anastrozole arm. Patients on treatment were to be re-consented and continue on anastrozole alone, OR taken off study.

Study treatment must be taken within 3 calendar days following randomization.

In the Randomized Phase, participants will be randomly assigned by an IRT system.

Palbociclib should be taken together with anastrozole as follows:

- Palbociclib is dosed QD PO for the first 3 weeks of the cycle (with the 4th week off). Anastrozole is dosed continuously, BID and QD PO, respectively.
- On scheduled visit days, participants must hold taking study treatments at home. They must take them in the clinic under the supervision of the Investigator or designee after all study procedures for the visit have been completed. On all other days, participants may take study treatments at home.
- Participants should be instructed to take palbociclib and anastrozole with a large glass of water (~250 mL or ~8 oz) at the same time each day.
- Palbociclib should be administered with food. Anastrozole can be administered either with or without food.
- Participants should be instructed to swallow the tablets whole and not to chew, crush, or open them.
- If vomiting occurs during the course of treatment, no re-dosing of the participant is allowed before the next scheduled dose. The occurrence and frequency of any vomiting during a treatment cycle must be noted in the AEs section of the eCRF.
- Any doses that are missed (not taken within 6 hours of the intended time) should be skipped and should not be replaced or made up on a subsequent day.
- Multivitamins, glucosamine, probiotics, and fish oil are permitted.

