9.1.3.1 Objective Response Rate Assessed by Imaging

ORR will be assessed at the end of the neoadjuvant treatment prior to Surgery.

For the purposes of this study, tumor response assessments will be performed by bilateral breast and axilla ultrasound (preferred) or mammography. Changes in tumor measurements and tumor responses will be assessed by the same Investigator or designee. The timepoint of tumor assessments will be reported on the eCRF based on the Investigator's assessment.

Radiographic Response Assessments:

- Radiographic complete response: Disappearance of the target lesion.
- Radiographic partial response (PR): At least a 30% decrease in the LD of the target lesion taking as reference the baseline LD.
- Radiographic progression (PD): At least a 20% increase in the LD of target lesion taking as references the baseline LD or the appearance of one or more new lesions.
- Radiographic stable disease (SD): Neither sufficient shrinkage to qualify for PR nor sufficient increase to qualify for PD taking as reference the baseline LD.

Note:

- 1) Target lesions should be selected on the basis of their size (lesions with the longest diameter) and should lend themselves to reproducible repeated measurements. Up to 2 lesions in the breast may be identified as target lesions. Per this protocol, target lesion #1 must be ≥ 2 cm and, if selected, target lesion #2 must be ≥ 10 mm. A sum of the diameters of all target lesions will be calculated and reported as the baseline sum of diameters. The baseline sum of diameters will be used as a reference to further characterize any objective tumor regression in the measurable dimension of the disease. Lesions that meet the criteria for radiographically defined simple cysts should not be considered malignant lesions (neither target nor non-target) since

they are, by definition, simple cysts. Pathologic axillary lymph nodes are not to be designated at target lesions, and lymph node measurements are not to be included in the sum of diameters.

[figure not shown]

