#### **7.5.4 Analysis of Objective Response Rate (ORR)**

One of the secondary objectives of the study is to estimate the ORR per investigator radiographic assessment in the treatment groups among all randomized subjects.

The number and percentage of subjects in each category of BOR per investigator assessment (complete response [CR], partial response [PR], stable disease [SD], progressive disease [PD], or not evaluable [NE]) will be presented, by treatment group. Estimates of response rate, along with its exact two-sided 95% and two-sided 90% CI by Clopper and Pearson will be presented, by treatment group.

- A by-subject listing of best overall response will be presented including treatment group, best overall response and dates of CR/PR/progression.
- A by-subject, by-visit, by-lesion listing of tumor assessment will be presented.

Similar analyses will be repeated based on the investigator clinical assessment of ORR. A by-subject listing of per time point tumor response per clinical assessment will be presented.

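### Clinical ORR has no scheduled palpation after Cycle 5 Day 1, so a response first palpable in the last cycle or before surgery can be missed; one mark in the Pre-surgery column closes the gap

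*Protocol*

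**What the plan says.** - Protocol Section 2, Table 2-2, efficacy rows: "Clinical breast examination by palpation of breast and axilla" is marked under Day 1 only. Days 8, 15 and 22 and the Pre-surgery column are empty for this row. Table 2-3 (follow-up) has no breast examination.
- Same table, imaging row: there is a mark in the Pre-surgery column, and the note asks for ultrasound (preferred) or "mammogram to be done on C2D22 and within 7 calendar days" before surgery.
- Same table, safety rows: the targeted physical examination is marked in the Pre-surgery column. Its note covers "Weight, BP, HR, temperature, and ECOG PS (Appendix 5) on Day 1 of each cycle" and an ocular examination. It does not mention breast or axilla.
- Protocol Section 4, Table 4-1: the objective is ORR, clinical and radiological, by investigator assessment. The endpoint is participants with a best response of CR or PR over those randomized, "for each treatment group at the end of the study treatment period".
- SAP 7.5.4: after the radiographic analysis, "Similar analyses will be repeated based on the investigator clinical assessment of ORR".
- SAP 4.2.2: best overall response is taken from randomization to progression, surgery or subsequent therapy. All available pre-surgery designations contribute, and confirmation is not required.

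**The concern.** Palpation is one of the two methods that Protocol 9.1.3 names for clinical response assessment, and a clinical ORR will be reported. Yet the schedule gives palpation no time point at or after the end of treatment, while imaging has one. The two versions of the same endpoint therefore stop looking at different times. If some tumors first meet response criteria on palpation during Cycle 5 or in the wait for surgery, imaging can count them and the scheduled palpations cannot. Clinical ORR would then be too low as a description of the whole neoadjuvant course, and part of any gap between the clinical and imaging rates could come from the schedule alone.

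**Working it through.** The plan states no figure to reproduce here. The check reads the schedule and works out dates.

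**Column alignment.** The targeted physical examination and imaging rows of Table 2-2 both show their Pre-surgery mark in the expected column. The empty Pre-surgery cell in the palpation row is therefore not a text-extraction artefact.

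**Dates.** Inputs are five cycles of 4 weeks (Protocol 5.1) and surgery within 4 weeks of the last dose (Table 2-2, footnote b). Study day = (cycle − 1) × 28 + day in cycle. The general ±3-day visit window is ignored.
- Last scheduled palpation, Cycle 5 Day 1: 4 × 28 + 1 = Day 113.
- End of Cycle 5: 5 × 28 = Day 140.
- Treatment days from the last palpation on: 140 − 113 + 1 = 28, and 28/140 = 20%.
- Surgery, if the last dose is on Day 140: Day 141 at the earliest, Day 140 + 28 = Day 168 at the latest.
- Last palpation to surgery: 141 − 113 = 28 days to 168 − 113 = 55 days.
- Last palpation to pre-surgery imaging: (141 − 7) − 113 = 21 days at the shortest, 55 days at the longest.

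**Order on the day.** Protocol 7.1.2 has the oral drugs taken in clinic "after all study procedures for the visit have been completed", and 7.1.1 starts nivolumab more than 1 hour after them. The Cycle 5 Day 1 palpation therefore precedes all Cycle 5 dosing.

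**What best overall response keeps and loses.** A CR or PR palpated at Cycle 2, 3, 4 or 5 Day 1 stays in the numerator. A CR or PR first palpable after Day 113 is lost unless someone makes an unscheduled examination. A progression first palpable after Day 113 also has no scheduled clinical record, but it would not remove a response already counted. The possible error in the responder count is therefore in one direction, downwards.

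**Effect per missed first response.** Denominators are the randomized arms, 40, 40 and 30 (Protocol 10.1).
- 1/40 = 2.5 points in Arms A and B.
- 1/30 = 3.3 points in Arm C.

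**Illustration.** The documents give neither the clinical ORR nor the number of late first responses. Assume 50% by Cycle 5 Day 1 in an arm of 40, with exact Clopper-Pearson 95% intervals:
- no late responders: 20/40 = 50% (33.8 to 66.2);
- two late responders: 22/40 = 55% (38.5 to 70.7);
- four late responders: 24/40 = 60% (43.3 to 75.1).

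Missing two to four late responders would shift the estimate by 5 to 10 points, against an interval about 32 points wide.

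**The case against.** The strongest reply is that clinical ORR is not a reading at Cycle 5 Day 1. It is a best response, and four scheduled post-baseline palpations already feed it. This stands. The 20% is calendar time after the last palpation, not the error in ORR, and the documents give no basis for estimating how many first responses come that late.

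Second, the clinical version is a repeat analysis. SAP 7.5.4 states its ORR objective on the radiographic assessment, which already has a pre-surgery time point, and it specifies no clinical-versus-imaging comparison. This also stands and limits the importance of the point.

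Third, the Table 4-1 timing phrase could refer to when participants are counted, not when they are examined. Even so, the SAP window runs to surgery, and the palpation schedule stops before that.

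A reader might also draw stronger conclusions that the documents do not support:
- **That the last cycle is never captured by palpation.** Protocol 9.1.3 allows tumor assessments at other times if clinically indicated, and an investigator could palpate at the pre-surgery physical examination. Neither is required, so the accurate statement is that no palpation is scheduled.
- **That participants who stop in Cycle 1 cannot be scored.** The denominator is all randomized participants, and not evaluable is a planned category, so they count as non-responders.
- **That the schedule treats Arms A and B unequally.** Both are palpated on the same days with one nivolumab dose outstanding at Cycle 5 Day 1 (4 of 5 given, 3 of 4 given). The study is non-comparative, and a later examination would not remove the phased start.
- **That Protocol 9.1.3.1 fixes the palpation date.** Its sentence "ORR will be assessed at the end of the neoadjuvant treatment prior to Surgery" stands under a heading about imaging.

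**Conclusion.** The gap is real but small. No clinical breast examination is scheduled between Cycle 5 Day 1 (Day 113) and surgery, so clinical ORR can be understated by 2.5 points (n = 40) or 3.3 points (n = 30) for each response first palpable after that visit and not picked up by chance. The total effect cannot be derived from the documents; it is zero if no first responses come that late. The dates assume on-time cycles and a last dose on Day 140. The primary RCB 0-I rate, pCR, breast-conserving surgery rate and radiographic ORR are unaffected. The change is worth making because it costs little and brings palpation into line with imaging, not because the trial's conclusions are at risk.

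**What to change.** In Protocol Table 2-2, mark Clinical Breast Examination in the Pre-surgery column (within 7 days before surgery) and state that the result is recorded in the eCRF as a tumor assessment. The recording instruction is needed because footnote d of that table says some assessments may not be captured as data. The last palpation would then be at most 7 days before surgery, against 28 to 55 days now for a participant who completes treatment.

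The SAP needs no new rule. Under SAP 4.2.2 the added examination enters best overall response as it stands, and one examination is enough because confirmation is not required. Clinical response should not be taken from this examination alone, since that would replace best overall response with a single time point and contradict SAP 4.2.2.

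The cost is a few minutes of palpation and one more eCRF entry per participant, at a visit that already includes a targeted physical examination. Participants who do not reach surgery would still lack a late palpation. If the schedule cannot be changed, SAP 7.5.4 should say that scheduled clinical assessments end at Cycle 5 Day 1.
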